TITLE:

Dose Intensification with a Focal Boost to Dominant Intraprostatic Lesion using Volumetric Modulated ArcTherapy /Image Guided Radiotherapy in Patients with Localized Prostate Cancer

ClinicalTrials.gov Identifier: NCT03030625 **Version**: 8, 18th November 2020

ABSTRACT:

Prostate cancer is a multi-focal disease and conventional therapies address this by treating the whole gland. However, numerous evidence coming from prostate pathology studies suggest the existence of a dominant cancer focus or dominant lesion (DL) within the gland that may be the nucleus of the aggressiveness of the cancer and therefore of recurrence post treatment. Thus strategies to identify and intensify treatment to this DL are under active investigation. Advances in multiparametric magnetic resonance imaging (mpMRI) have shown promising results in identifying focal lesions and advances in high accuracy radiotherapy have enabled dose intensification.

Hypothesis

The hypothesis is that differential boosting with focal dose escalation delivered by VMAT to an imaging (mpMPR) defined DL within the prostate is associated with a higher PSA, clinical (mpMRI) and histological control without a significant increase in toxicity (both acute and late) in males with localized prostate.

Objectives

The aim of this study was to determine the efficacy and safety of the implementation of a program of " image-guided focal Intensification dose to intraprostatic dominant lesion " in men with localized prostate cancer (PCa) of intermediate and high risk (criteria NCCN) eligible to receive radiotherapy in the Department of Radiation Oncology of HUP within the established dose escalation protocol with intensity modulated image-guided radiotherapy (IMRT / IGRT).

Primary objectives:

- To increase biochemical and local control of patients localized PCa of intermediate and high- risk.

- To maintain or decrease the incidence of acute and late urinary rectal complications despite increased dose (focal) radiotherapy.

Secondary objectives:

- Biochemical disease-free survival at 3 yrs (according to RTOG-ASTRO Phoenix Consensus Conference criteria).

- Assessment of the quality of life perceived by the patient in the urinary, digestive and hormone domains.

- To determine the impact of treatment on the disease-free survival (DFS).

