- To assess the adequacy of the safety margins of the treatment volume and the possibility of reducing these margins to minimize the risk of complications when incorporating specific immobilization.

SAMPLE SIZE 37 PATIENTS

STUDY VARIABLES DEFINITION

- 1. Patients were counted as biochemical failures according to the Phoenix definition (PSA >2 ng/mL above the currently observed PSA nadir). The Kaplan- Meier method was used to estimate the probability of biochemical control and of DFS.
- 2. Biochemical relapse-free survival (bRFS) was calculated from the time of first radiation treatment to failure, last follow-up or death. PSA nadir was set to be the lowest PSA value following treatment completion. Benign bounce was defined as nadir +0.2 ng/ml as long as subsequent PSAs after the bounce dropped lower than the relative nadir before the bounce.
- 3. Morphological and functional response was evaluated by mpMRI at 12 months after radiotherapy and compared to the baseline scans.
- 4. Acute toxicity was assessed in terms of the incidence and severity of genitourinary (GU) and gastrointestinal (GI) adverse events from 48 h until 3 months after the procedure.
- 5. Late toxicity defined as the maximal toxicity per patient more than 90 days after completion of RT Late adverse effects of radiation assessed at each follow-up visit using the radiation morbidity scoring criteria of the European Organization for Research and Treatment of Cancer Radiation Therapy Oncology Group (EORTC/RTOG) and The Common Terminology Criteria for specific Adverse Events.

The incidence of late adverse effects was calculated as the occurrence of the maximum grade toxicity per patient divided by the number of patients in each arm. The c2 or Fisher exact test was used to evaluate differences in patient and treatment characteristics for categorical variables. The t test, analysis of variance, or Mann-Whitney test was used, depending on the type and distribution of the variables, to evaluate differences in patient and treatment characteristics for continuous data. The cumulative incidence method was used to estimate time to late toxicity, and treatment groups were compared using the log-rank test. Death from any cause was considered a competing risk.

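### The plan compares arms and treatment groups that it never defines, so the log-rank test cannot be run as written and the comparative hypothesis cannot be concluded

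*Combined protocol and SAP*

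**What the plan says.** The paragraph after item 5 of STUDY VARIABLES DEFINITION contains three elements that presuppose groups:

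- Late adverse effects are the maximum grade per patient, "divided by the number of patients in each arm".
- Differences in patient and treatment characteristics are tested by chi-square or Fisher's exact test (categorical data) and by t test, analysis of variance or Mann-Whitney (continuous data).
- "The cumulative incidence method was used to estimate time to late toxicity", after which "treatment groups were compared using the log-rank test". The paragraph adds: "Death from any cause was considered a competing risk".

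The whole sample-size statement is "SAMPLE SIZE 37 PATIENTS".

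Under Hypothesis, the focal boost "is associated with a higher PSA, clinical (mpMRI) and histological control without a significant increase in toxicity (both acute and late"). Of the two primary objectives, one is to increase biochemical and local control, and the other is to keep urinary and rectal complications at the same level or lower. The general aim, under Objectives, is to determine the efficacy and safety of introducing the programme.

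Other analyses need no second group. In item 1 the Kaplan-Meier "method was used to estimate the probability of biochemical control and of DFS". In item 3, mpMRI at 12 months is compared with each patient's baseline scan.

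**The concern.** A between-group test needs groups, and a claim of higher control or no increase in toxicity needs something to measure against. The document names neither.

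Two possible references are in the background. The Abstract notes that "conventional therapies address this by treating the whole gland", and the Objectives place the study within the department's existing dose-escalation protocol. The first is background and the second is the setting. Neither comes with a cohort, a rate or a margin.

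The gap reaches the hypothesis and both primary objectives. If higher control or no significant increase in toxicity were later claimed against a reference chosen after outcomes were known, readers could not tell a planned comparison from a post hoc one.

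**Working it through.** **1. The plan's own figure.** The only figure is N = 37. It can be neither reproduced nor refuted, because the document gives no alpha, power, effect size, reference rate, margin or allocation ratio.

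**2. Which analyses need groups, and whether any are defined.**

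| Element | Needs | Defined in the document |
|---|---|---|
| Late-toxicity incidence per arm | arms | no |
| Chi-square/Fisher, t test, ANOVA, Mann-Whitney on characteristics | at least two groups | no |
| Log-rank on time to late toxicity | at least two groups | no |
| Higher control (Hypothesis; first primary objective) | reference group or rate | no |
| No significant increase in toxicity (Hypothesis; second primary objective) | reference and margin | no |
| mpMRI at 12 months against baseline | each patient's own baseline | yes |
| Kaplan-Meier for biochemical control and DFS | one cohort | yes |
| Cumulative incidence of late toxicity, death competing | one cohort | yes |

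**3. The log-rank with one group.** At each event time j, with d_j events among n_j at risk, group i has expected count d_j × n_ij/n_j. With a single group n_ij = n_j, so observed minus expected is d_j − d_j = 0. The variance term contains (1 − n_ij/n_j) = 0, and the degrees of freedom are 1 − 1 = 0. The statistic is 0/0 and undefined. A software check on one simulated group of 37 returned an error.

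**4. The one comparison with a stated reference.** The change in mpMRI from baseline to 12 months is within-patient. It can show that lesions responded. It cannot show that control is higher than it would have been without the boost.

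**5. What 37 patients can estimate (illustration).** Exact two-sided 95% limits for x events in n patients are the 0.025 quantile of Beta(x, n − x + 1) and the 0.975 quantile of Beta(x + 1, n − x). For x = 0 the upper limit is 1 − 0.025^(1/n); with n = 37 this is 1 − 0.905 = 9.5%. The event counts are chosen for illustration, and censoring and competing death are ignored.

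| Result | Estimate | Exact 95% CI |
|---|---|---|
| Toxicity 0/37 | 0% | 0 to 9.5% |
| Toxicity 3/37 | 8.1% | 1.7 to 21.9% |
| Control 35/37 | 94.6% | 81.8 to 99.3% |

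If only 30 or 25 patients were assessable (an assumption; the document gives no figure), zero events would have an upper limit of 11.6% or 13.7%, and three events would give 2.1 to 26.5% or 2.5 to 31.2%.

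**The case against.** - **The objectives are programme goals, and the aim is estimation.** This is fair in part. The stated aim fits estimation, and the primary objectives can be read as aspirations. The hypothesis cannot be read that way as easily: absence of a significant increase is a statistical claim, and the same document specifies a between-group test for late toxicity.
- **A single-arm study is legitimate.** It is. Nothing here calls for a control arm or for more patients.
- **Groups may exist without being described.** This stands. The per-arm denominator, the reference to treatment groups and the tests of treatment characteristics (including ANOVA, usually chosen for more than two groups) would fit a concurrent or historical control, or subgroups of the 37. Once groups are named, the log-rank becomes computable.
- **The confidence intervals do not measure the defect.** Correct. They would be the same if a comparator were perfectly defined. They show only what a cohort of this size can say.

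A reader might also infer that the per-arm wording is simply a slip in a single-arm plan. The document never says the study is single-arm, so that is only one of the possible readings. Nor can the trial be called underpowered on this text: a power figure would need a split, an effect and an error rate that the plan does not give.

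**Conclusion.** The point holds and needs correction. The number of arms is unclear. As written, the log-rank test cannot be run, the tests of characteristics have no groups to compare, and the late-toxicity denominator is undefined. Neither higher control nor absence of an increase in toxicity can be concluded from this plan.

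This rests on the text alone and on no assumed rate or power figure. The intervals in the working are illustrations that depend on the chosen event counts and on complete follow-up.

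Two stronger readings are tempting. One is that the whole analysis fails. It does not: the Kaplan-Meier estimates, the cumulative incidence of late toxicity and the within-patient mpMRI comparison can all be carried out in one cohort. The other is that a comparator was picked after the results were seen. The document does not show that this happened; it shows only that the plan offers no protection against it.

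**What to change.** 1. **State whether the study is single-arm.** If it is, delete the log-rank comparison and the group tests of characteristics, describe the characteristics instead, and use all treated patients as the late-toxicity denominator. If groups exist, define them, their source or allocation, and their sizes.
2. **For a single cohort, state the primary objectives as estimation:**
   - biochemical control by Kaplan-Meier with a 95% CI at 3 years, the time the Objectives already give for biochemical disease-free survival;
   - local control from the 12-month mpMRI response, as a proportion with an exact 95% CI, which requires saying what counts as a response;
   - incidence of acute and late GU and GI toxicity with exact 95% CIs;
   - cumulative incidence of late toxicity with death as a competing risk and a 95% CI.
3. **Limit comparative conclusions.** Do not conclude higher control or no significant increase in toxicity unless each endpoint has a sourced reference value that was fixed before outcomes were reviewed. Otherwise label the comparison post hoc.
4. **Document the change.** Because this is version 8 with methods in the past tense, keep the existing hypothesis and objectives visible and date the revision.
5. **State the precision of 37 patients,** as illustration only.

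**Cost.** For a single cohort the change needs no extra patients, visits or procedures. It does mean a more modest claim and a documented, dated change to the objectives. Keeping a comparison requires a sourced reference, and at this stage it may have to be reported as post hoc.
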